## 1. Overview

- a. Study Title: Aging with Pride: Innovations in Dementia Empowerment and Action
- b. Research Site: University of Washington
- c. Objectives: Healthy People 2020 identified sexual/gender minority older adults as a health disparate population. The lack of efficacious research-based interventions for such vulnerable older adults with Alzheimer's disease and related dementias (AD/RD) and their care partners (CPs) is a significant public health problem. AD/RD will affect up to four million sexual/gender minority older adults with AD/RD and their CPs. These older adults are underserved with significant barriers to healthcare access and the lack of culturally competent care. Caregiving of sexual/gender minority older adults with AD/RD is of concern due to social stigma, marginalization, and isolation, which may be barriers to sustaining caregiving. It is necessary and timely to translate evidence-based culturally adaptable interventions for this underserved and stigmatized population. Reducing Disability in Alzheimer's Disease (RDAD) has been evaluated in a randomized controlled trial and has shown to successfully train community-dwelling CR-CP dyads to increase the physical activity and functioning of individuals with AD/RD, as well as their CPs. It also teaches CPs techniques for managing behavioral symptoms of CRs. RDAD consequently decreases stress of CPs, delays institutionalization of CRs, and increases HRQOL of CRs and CPs. Thus, this study will evaluate the effect of RDAD among CRs with AD/RD and their CPs in the sexual/gender minority population, and this study will test an enhanced RDAD tailored to better respond to distinct sexual/gender minority risks experienced by CPs and CRs with AD/RD, addressing unique sexual/gender minority risk factors (e.g., identity management, stigma-related adverse or traumatic life events, and lack of social support). The enhanced RDAD will be referred to as Aging with Pride: Innovations in Dementia Empowerment and Action (IDEA). We will address the following aims:
  - a. Aim 1. Test the translation of RDAD and IDEA programs designed to increase physical activities of older adult care receivers (CRs) with AD/RD and their CPs. Aim 2. Evaluate the short- and long-term effect of RDAD and IDEA on primary (*physical activity for CRs*) and secondary outcomes (*memory-related behavioral disturbances, physical functioning, and QOL for CRs; depressive symptomatology; perceived stress for CRs*). Aim 3. Test the moderating roles of CR-CP characteristics and severity of CR AD/RD on the treatment effect of RDAD and IDEA.
  - b. Study design: This study will utilize a 2-group randomized, single blind with staggered multiple baseline design and three follow-up assessments.

c. Background: Lesbian, gay, bisexual, and transgender (LGBT) older adults are an at-risk, underserved, and rapidly growing population with elevated risk for AD/RD. RDAD, which is grounded in social-learning and gerontological theories, is a present-focused cognitive-behavioral intervention aimed at increasing physical activity and problem-solving while engaging both members of CR-CP dyad. The focus of problem-solving in RDAD is specific to the needs of the CR and CP. The standard RDAD, however, has not been translated to a highly stigmatized and marginalized population, such as LGBT older adults, with unique CR-CP characteristics. Our previous findings indicate that exercise programs for older adults with AD/RD have been found to be more effective for caregiving dyads with a married spouse as caregiver. LGBT older adults, however, are less likely to be married and a significant proportion of caregivers in this population are friends (not family). Moreover, discrimination and stigma across the life course necessitate continual identity management for many LGBT older adults (e.g., nondisclosure of LGBT identity in contexts in which it would be unsafe to disclose or would reduce access to resources and services). These processes may be complicated by cognitive decline in ways that increase stress. For example, with advanced memory decline the CR may inadvertently disclose to an intolerant family member or provider from whom they had previously concealed their identity, resulting in conflict or interpersonal discomfort that the CP must manage and negotiate. Thus, it is essential to address the unique CR-CP characteristics in RDAD to improve treatment effects. This study will extend and test the RDAD intervention with the sexual/gender minority population, and will also develop and test Aging with Pride: Innovations in Dementia Empowerment and Action (IDEA), a modified version of RDAD tailored to better respond to distinct risks experienced by CPs and CRs with AD/RD in the sexual/gender minority population.

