Potential participants may contact the study by phone, email or through an on-line prescreen. Potential participants who learn about the study through the study website and complete a pre-screen are asked if they prefer to be contacted by phone, email or text. Study staff contact potential participants using their preference, following an approved script. Potential participants who email the study receive an email reply asking them to call the study phone number and leave a message if the call is not answered. Study staff return calls from potential participants who leave a message and if the potential participant is not reached leave a brief message reminding them about the study and request that they call back. Study staff will reach CP potential participants by phone so that they can answer CR and CP eligibility screening questions with a staff member to determine eligibility based on the inclusion and exclusion criteria.

We will use Trialfacts to promote, screen and refer eligible participants for the IDEA project. Trialfacts provides patient recruitment services for clinical trials. Ads may run on a combination of platforms including but not limited to: Facebook, Google, Google Display Network, Yahoo, Bing, Instagram, Youtube, Reddit, and Quorra. The ads will be linked to the Trialfacts landing page, which in turn is linked to the online questionnaire. Potential participants who complete the on-line screening will schedule a telephone interview with Aging with Pride: IDEA study staff to confirm their eligibility.

- b. Recruitment Materials: Study announcements will be distributed by mail and email using aging and health service agencies' contact lists and will be posted at various health, human service and community-based organizations, and published in community-based newspapers, newsletters, and social media. A short 2-minute video will be on the study webpage and a link will be put in our social media announcements. Upon expressing interest in participating, initial screening of eligibility of CPs and CRs will be conducted by telephone using a script including the purpose and design of the study, a brief review of key elements of the consent form, and an eligibility screen assessment form.
4. Study Procedures:

- a. A total of 150 CR/CR dyads will be recruited from all 50 U.S. states and territories and randomly assigned to one of two treatment arms: IDEA (75) or RDAD (75).

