- b. Pre-Treatment (baseline) assessment: Pre-treatment (baseline) assessments #1 and #2: Upon the random assignment, a research coordinator will contact subjects and schedule two pre-treatment assessments with a 6-week interval via telephone. CP will complete a 40 to 60-minute questionnaire via telephone for each assessment.
- c. Interventions: RDAD and IDEA are 9 1-hour sessions, conducted over 6 weeks in the participants' homes or a place of their choice where privacy is ensured. The sessions will be conducted twice a week for the first three weeks; once a week for the next three weeks; in the 12-week maintenance phase 4 15- minute follow-up phone calls will occur once a month for the next 4 months.

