exception being incidents of abuse of a dependent adult or minor child and risks of imminent harm to others or to the subject. All researchers have completed training in research with human subjects.

10. Analysis Plan: All participant data will be included in the study, according to the intent-to-treat principle, after excluding participants who withdrew prior to completing their baseline assessment. Analysis will be completed using Stata/MP 16.1 (StataCorp, 2019). To assess whether randomization of patients was successful, the two treatment groups will be compared by baseline demographics and clinical characteristics using two-sample *t*-tests, Chi-Square tests of independence, or Fisher's exact tests as appropriate. To test efficacy of the interventions, we will use linear mixed models to test the short- and long-term intervention effects on outcomes, with time treated as a categorical variable. The models included random intercepts and slopes for each participant to account for individual variability at baseline and change over time of the outcome variables and included baseline scores of the outcomes as fixed effects. Mixed-effects logistic regression models were estimated for binary outcomes, and continuous outcomes were estimated with mixed-effects linear regression models. Moderation effects were evaluated using interaction terms in the linear mixed models. The proposed sample size with a two-sided significance of 5% and a statistical power of 80% is sufficient to detect a small effect ( $d= 0.25$ ), which is greater than a minimal clinically important difference level. The statistical significance of all hypothesis tests were set at two-sided level of  $p = .05$ .

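### Caregiver relationship, which the protocol's own background ties to exercise response, is not prespecified as a covariate in the efficacy models or named as an Aim 3 moderator: a modest, nearly free precision gain is forgone

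*Combined protocol and SAP*

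**What the plan says.** Section 1.c states, from the team's previous findings, that "exercise programs for older adults with AD/RD have been found to be more effective for caregiving dyads with a married spouse as caregiver". It goes on to say that LGBT older adults are less often married and that a sizeable share of their caregivers are friends. It gives no effect size and no expected relationship mix.

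Section 4.a assigns 150 dyads at random, 75 to IDEA and 75 to RDAD. It describes no randomisation method: no strata, blocks or minimisation. Section 4.b places assignment before the baseline visits: "Upon the random assignment, a research coordinator will contact subjects and schedule two pre-treatment assessments with a 6-week interval via telephone".

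Section 4.c describes one exercise programme for both arms. IDEA works its LGBT-specific content into the existing training so that time and exposure match RDAD.

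On analysis, section 10 says that the mixed models "included baseline scores of the outcomes as fixed effects". No other adjusting covariate is named. The arms are to be compared on baseline characteristics by significance tests, and no rule follows for acting on a difference. Aim 3 is to "Test the moderating roles of CR-CP characteristics and severity of CR AD/RD on the treatment effect of RDAD and IDEA", and section 10 adds: "Moderation effects were evaluated using interaction terms in the linear mixed models". Neither place lists the moderators by name.

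**The concern.** A factor that changes the response to an exercise programme predicts follow-up exercise days wherever that programme is delivered, and here it is delivered in both arms. The effect that section 1.c describes arises after treatment starts, so a pre-treatment count of exercise days is unlikely to carry all of it. If relationship is left out of the efficacy model, the variance it explains stays in the error term, and any chance difference in spouse share between arms moves this trial's own estimate.

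Prespecification matters too. Section 10 tests for baseline differences but does not say what happens if one is found. A visible imbalance in spouse caregivers would then leave the decision to adjust until after the data are seen. Naming the covariate in advance removes that choice.

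**Working it through.** **The plan's own figure.** Section 10 claims 80% power for d = 0.25 at two-sided 5%. For one follow-up visit without covariates, SE = sqrt(2/75) = 0.163 SD and power = Φ(0.25/0.163 − 1.96) = 33.4%. The 80% is not reproduced on that simple basis. It could be reached with several follow-ups and a high enough correlation between visits, but no correlation is stated. That is a separate matter, and the present point does not depend on it. The 33.4% serves below only as a reference.

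**Inputs.** From the documents: 75 dyads per arm, two-sided 5%, d = 0.25. Assumed, because the documents do not give them: spouse share q = 30-50%, and a spouse-versus-other difference at follow-up of b = 0.3-0.5 SD, the same in both arms.

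**Variance explained.** v = q(1 − q)b².
- Low end: 0.3 × 0.7 × 0.3² = 0.0189.
- High end: 0.5 × 0.5 × 0.5² = 0.0625.

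So relationship explains about 2-6% of outcome variance. The equivalent gain in sample size is v/(1 − v): 0.0189/0.9811 = 1.9% to 0.0625/0.9375 = 6.7%, about 2-7% more dyads. Reference one-visit power rises from 33.4% to between 33.9% and 35.2%. With wider assumptions (q = 20-70%, b = 0.2-0.5 SD), v runs from 0.6% to 6.3%.

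**Probability of imbalance.** If K of the 150 dyads have a spouse caregiver and k of them fall in one arm, k is hypergeometric and the difference in shares is (2k − K)/75. A difference of at least 10 points needs |2k − K| of at least 8 when K is even and at least 9 when K is odd.

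| K | Share | P(difference ≥ 10 points) |
|---|---|---|
| 45 | 30.0% | 15.4% |
| 46 | 30.7% | 21.5% |
| 60 | 40.0% | 24.3% |
| 61 | 40.7% | 18.3% |
| 75 | 50.0% | 19.1% |

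The jumps between neighbouring rows come from odd versus even counts, so only the rough range of 15-25% should be used. A normal approximation, with imbalance SD = sqrt(q(1 − q) × 2/75) = 7.5 to 8.2 points, gives 18-22%.

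**Shift from a 10-point imbalance.** 0.10 × 0.3 = 0.03 SD to 0.10 × 0.5 = 0.05 SD. That is 12-20% of d = 0.25, and 18-31% of the one-visit standard error of 0.163.

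**Type I error.** In the unadjusted model the relationship variance widens the standard error to sqrt((2/75)(1 + v)), with residual SD 1. Given a 10-point imbalance, the false-positive rate is Φ(−1.96·sqrt(1 + v) + s) + Φ(−1.96·sqrt(1 + v) − s), with s = 0.10b/0.163. For q = 0.3 and b = 0.3, this is Φ(−1.978 + 0.184) + Φ(−1.978 − 0.184) = 5.2%. Over the assumed range it is 5.1-5.4%. With balanced arms (s = 0) it is 4.3-4.8%, and over all allocations it is 5.0%. A simulation of 20,000 trials per setting, at q = b = 0.3 and q = b = 0.5, gave 5.1% unadjusted and 5.1-5.2% adjusted. The mean estimate was on target both ways.

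**The case against.** The strongest reply has four parts.

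1. **Randomisation already allows for chance imbalance.** This stands. A reader might infer that an imbalance in spouse share biases the IDEA-RDAD contrast or inflates its false-positive rate. The calculation does not support that: the unadjusted standard error already contains the relationship variance, and the overall error rate stays at 5%.

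2. **The documents do not say that randomisation is unstratified.** This also stands. Section 4.a is silent on the method, so a reader can say only that no stratification is described.

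3. **The gain is small and rests on unseen inputs, and adjusting for baseline alone is acceptable practice.** Section 1.c gives a direction and no size, so the gain could be below the figures shown. Leaving out one covariate is not an error. This limits the weight of the point but does not remove it, because the change costs almost nothing and the protocol itself singles out this characteristic.

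4. **Aim 3 already handles it.** IDEA adds social-support building, so the spouse gap might be smaller under IDEA than under RDAD. That would be an interaction, which Aim 3 is meant to test, and such a model would normally carry the moderator's main effect. It would be too strong, then, to say that the plan has no place for relationship. But an Aim 3 model does not adjust the Aim 2 efficacy contrast, and neither Aim 3 nor section 10 names relationship as a moderator.

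**Conclusion.** The point holds as a recommendation about precision and prespecification. The protocol supplies its own reason to expect caregiver relationship to be prognostic, yet section 10 does not name it as a covariate in the efficacy models or as a moderator. The expected loss is modest: about 2-6% of outcome variance. The shift of 0.03-0.05 SD applies only if a 10-point imbalance occurs. These sizes rest on a spouse share, an effect size and an equal effect in both arms that are assumed here, not documented. The main comparison remains valid without the change.

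**What to change.** In section 10, prespecify caregiver relationship as a fixed effect in every efficacy model, recorded no later than the pre-treatment assessments, and name it as an Aim 3 moderator. Define the categories in advance and say where unmarried partners fall. Section 7.f notes that families of choice often include partners without legal recognition, so a bare split of married spouse against everyone else would group them with friends.

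The cost is one or two degrees of freedom, depending on the number of categories, and no extra dyads or visits. Aim 3 plausibly needs the variable in any case.

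Stratified randomisation is optional. It could apply only to dyads still to be randomised, and only if relationship is recorded at the telephone screen, because assignment precedes the baseline assessments and section 2.b does not list relationship type among the eligibility items. Section 10 mixes future and past tense, so the documents do not show whether any dyads remain to be assigned. The covariate is useful either way.

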## 2. Participants

- a. General characteristics: 150 dyads of CRs with AD/RD aged 50 or older and their CPs (N=300) will participate in the study. Either the CR or CP will be sexual/gender minority.
- b. Inclusion Criteria: Inclusion criteria for CR and CP: Either CR or CP is a sexual or gender minority. Inclusion criteria for CR: 1) age at enrollment is 50 years of age or older; 2) living in the community (not in a long-term care facility with nursing home level care); 3) have Alzheimer's disease or other dementia. Based on the definition of dementia suggested by Alzheimer's Association and scientific literature, dementia will be determined 1) by asking CP the current diagnostic

status of CR's AD/RD or 2) by asking CP whether CR has any difficulties in the domains of dementia/memory loss AND needs any help in daily activities. This method has two key aspects: (1) it precludes considerable increased costs that would be necessitated by providing a physical exam and (2) avoids unnecessary delays (and potentially loss of subjects) by scheduling an exam or waiting for receipt of patient charts. Inclusion criteria for CP: 1) willing to spend at least 30 minutes per day for study activities or willing to coordinate with CR's networks to do so; 2) providing care to the CR; 3) living in the community, not in a nursing home or long-term care facility.

- c. Exclusion Criteria: Exclusion criteria for CR and CP: 1) having plans to move to a long-term care setting within 6 months of enrollment; 2) having a known terminal illness (with death anticipated within the next 12 months); 3) having been hospitalized for a psychiatric disorder in the 12 months prior to baseline; 4) actively being suicidal and having major hallucinations or delusions (occasional hallucinations or delusions are common symptoms of dementia. CR will be eligible if CR's hallucinations or delusions do not prevent participation in a low impact exercise); and 5) having any physical limitations/chronic conditions preventing participation in a low impact exercise program.
- d. Number of Subjects: 150 dyads (N=300)
  - i. IDEA Intervention Arm: 75 CR/CP dyads
  - ii. RDAD Intervention Arm: 75 CR/CP dyads

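### Exclusion 4 joins active suicidality and major hallucinations or delusions with *and* in one item; split it so that suicidality clearly excludes on its own

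*Combined protocol and SAP*

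**What the plan says.** Section 2.c lists five exclusions that apply to both members of the dyad. Item 4 is "actively being suicidal and having major hallucinations or delusions". A parenthesis follows it. It notes that occasional symptoms of this kind are common in dementia and keeps a CR eligible if the CR's "hallucinations or delusions do not prevent participation in a low impact exercise". The parenthesis mentions neither suicidality nor the CP.

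The neighbouring items are item 3, "having been hospitalized for a psychiatric disorder in the 12 months prior to baseline", and item 5, "having any physical limitations/chronic conditions preventing participation in a low impact exercise program". Items 1 and 2 deal with a planned move to long-term care and with terminal illness.

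Section 3.a says how the criteria are applied. Staff reach the CP by telephone "so that they can answer CR and CP eligibility screening questions with a staff member to determine eligibility based on the inclusion and exclusion criteria". People who come through the outside recruiter's online questionnaire "will schedule a telephone interview with Aging with Pride: IDEA study staff to confirm their eligibility". Section 3.b mentions a screening script and an eligibility form; neither is among the documents.

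**The concern.** Two separate psychiatric conditions share one number and are joined by *and*, while the same phrase uses *or* between hallucinations and delusions. A screener who applies the words as written could conclude that a person must have both conditions to be excluded. The person let through would then be someone who is actively suicidal but not psychotic, which is the case a suicidality exclusion most obviously exists to catch.

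The placement of the parenthesis adds a second difficulty. It qualifies the whole of item 4, so its statement that the CR is eligible when symptoms do not prevent exercise is not expressly confined to the hallucinations-or-delusions half. Nothing there says that suicidality still excludes such a CR.

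This matters because section 3.a makes the written criteria the screening standard, and the CP answers for both members. If a form repeats item 4 as a single question, a *no* does not show that each condition was ruled out. The intervention and assessments also touch on distressing material: section 9.a anticipates psychological discomfort from questions on adverse experiences, and section 4.c.ii builds stigma-related traumatic events into the IDEA arm.

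**Working it through.** There is no figure to reproduce. The check compares what each reading does and then asks whether another criterion fills any gap.

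**The two readings of item 4**
- *List reading:* either condition excludes on its own, subject to the CR allowance for hallucinations or delusions.
- *Literal reading:* both conditions must be present.

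**Who is excluded by item 4**

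| Profile | List reading | Literal reading |
|---|---|---|
| CR or CP: suicidal, no major hallucinations or delusions | Excluded | Not excluded |
| CP: major hallucinations or delusions, not suicidal | Excluded | Not excluded |
| CR: major hallucinations or delusions, not suicidal | Excluded only if symptoms prevent low-impact exercise | Not excluded by item 4; item 5 may exclude if symptoms prevent exercise |
| CP: both | Excluded | Excluded |
| CR: both, symptoms do not prevent exercise | Excluded for suicidality, if the parenthesis is confined to hallucinations or delusions | Eligible, if the parenthesis governs the whole item |
| CR: both, symptoms prevent exercise | Excluded | Excluded |

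**Does another criterion fill the gap?**
- Items 1 and 2 concern residence plans and terminal illness, so they do not.
- Item 3 needs a psychiatric hospitalization within 12 months before baseline. A person who is actively suicidal but has not been hospitalized is outside it.
- Item 5 turns on ability to do low-impact exercise. Suicidality need not affect that.
- The inclusion criteria in section 2.b cover age, residence, dementia status, the caregiving role, time available and sexual or gender minority status. None concerns suicidality.

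Suicidality therefore appears as an entry rule only in item 4.

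**Where the reading matters little.** For a CR with hallucinations or delusions only, the list reading already allows entry unless symptoms prevent exercise. Under the literal reading, item 5 may exclude much the same people: every CR has dementia, a chronic condition, and the parenthesis treats occasional hallucinations and delusions as common symptoms of it. This depends on reading item 5 to include such symptoms, which its wording permits but does not state.

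**Scope.** The item applies to 150 dyads × 2 members = 300 people, and to everyone screened. That is the reach of the rule, not a count of people affected.

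**The case against.** The strongest reply is that the text largely settles the matter. The parenthesis deals with hallucinations and delusions without mentioning suicidality. Such an allowance makes most sense if those symptoms can exclude by themselves, since under a joint requirement a non-suicidal CR with hallucinations would not need it. The five exclusions are also cumulative, so *and* can naturally add one ground to another. This stands: either condition is very probably meant to exclude.

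A reader might look to the dementia definition in section 2.b, "has any difficulties in the domains of dementia/memory loss AND needs any help in daily activities", as evidence that *and* in this section means both. It does not help that reading. The definition capitalises the word to mark a joint requirement and item 4 does not, so the contrast points towards separate grounds. The ambiguity rests on the wording of item 4 itself and on the absence of any other suicidality criterion.

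It is also fair to say that the eligibility form may already ask about the two conditions separately, and that study staff confirm eligibility after the recruiter's online screen. There are protections after entry: section 9.b has coaches monitor distress, contact the investigators and start a referral where needed, section 9.d makes risk of imminent harm an exception to confidentiality, and section 4.c.i has CP depression assessed during the programme. These reduce the consequence. They act after enrolment, though, and do not make the entry rule clear.

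**Conclusion.** The point holds as a minor, safety-relevant wording correction. Three groups depend on how item 4 is read: a suicidal CR or CP without major hallucinations or delusions, a CP with major hallucinations or delusions who is not suicidal, and a suicidal CR whose symptoms do not prevent exercise. For a CR with hallucinations or delusions only, the outcome is largely the same either way.

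The number of people affected cannot be estimated, because the documents give no rates of suicidality or psychosis and the screening form is not included. If the form already asks the two questions separately, the number wrongly admitted through this wording is zero.

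A reader might infer that ineligible people have been enrolled, or that the plan deliberately admits suicidal participants. The documents support neither: they show an unclear rule whose probable intent is sound. Sample size, power, the significance level and the analysis are not affected.

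**What to change.** Divide item 4 into two numbered grounds, each excluding on its own, for both CR and CP:
- *4a:* actively suicidal.
- *4b:* major hallucinations or delusions, with the allowance for a CR whose symptoms do not prevent low-impact exercise attached here only.

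Then check that the telephone eligibility form, the website pre-screen and the recruiter's questionnaire ask about the two separately wherever they cover them, and amend only those that do not. If both conditions really are meant to be required together, say so and give the reason.

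The cost is a one-sentence amendment, a review of the forms and possibly a few more screen failures.
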